10.2 Additional Safety Monitoring

10.2.1 Liver safety monitoring

To ensure patient safety and enhance reliability in determining the hepatotoxic potential of an investigational drug, a standardized process for identification, monitoring and evaluation of liver events has to be followed.

The following two categories of abnormalities / adverse events have to be considered during the course of the study (irrespective of whether classified/reported as AE/SAE):

- Liver laboratory triggers, which will require repeated assessments of the abnormal laboratory parameter
- Liver events, which will require close observation, follow-up monitoring and contributing factors are recorded on the appropriate CRFs

Please refer to [Table 16-1](#) in Appendix 2 for complete definitions of liver laboratory triggers and liver events.

Every liver event defined in [Table 16-1](#) should be followed up by the investigator or designated personnel at the trial site, as summarized below. Additional details on actions required in case of liver events are outlined in [Table 16-2](#). Repeat liver chemistry tests (i.e. ALT, AST, TBL, PT/INR, ALP and G-GT) to confirm elevation.

- These liver chemistry repeats will be performed using the central laboratory. If results will not be available from the central laboratory, then the repeats can also be performed at a local laboratory to monitor the safety of the patient. If a liver event is subsequently reported, any local liver chemistry tests previously conducted that are associated with this event should have results recorded in source documents.
- If the initial elevation is confirmed, close observation of the patient will be initiated, including consideration of treatment interruption if deemed appropriate.
- Discontinuation of the investigational drug (refer to the Discontinuation of study treatment section), if appropriate
- Hospitalization of the patient if appropriate
- Causality assessment of the liver event
 - Other investigations can include, based on investigator's discretion: serology tests, imaging and pathology assessments, hepatologist's consultancy; obtaining more detailed history of symptoms and prior or concurrent diseases, history of concomitant drug use, exclusion of underlying liver disease

All follow-up information and procedures performed must be recorded as appropriate in the CRF.

Refer to Appendix 2 ([Section 16.2](#)) and the SOM for additional details.

10.2.2 Renal safety monitoring

The serum creatinine will be used to monitor for renal injury. A serum creatinine increase $\geq 25\%$ compared to baseline during normal hydration status is considered a renal event and should be followed up by the investigator or designated personnel at the trial site as summarized in [Section 16.3](#) (Appendix 3). Abnormal renal event findings must be confirmed ≥ 24 hours but ≤ 5 days after first assessment.

Refer to [Section 16.3](#) (Appendix 3) and the Site Operations Manual for additional details.

11 Data Collection and Database management

11.1 Data collection

All data should be recorded, handled, and stored in a way that allows its accurate reporting, interpretation, and verification.

Designated investigator staff will enter the data required by the protocol into the Electronic Case Report Forms (eCRF). The eCRFs have been built using fully validated secure web-enabled software that conforms to 21 CFR Part 11 requirements. Investigator site staff will not be given access to the EDC system until they have been trained. Automatic validation programs

check for data discrepancies in the eCRFs and allow modification and/or verification of the entered data by the investigator staff.

The investigator/designee is responsible for assuring that the data (recorded on CRFs) (entered into eCRF) is complete, accurate, and that entry and updates are performed in a timely manner. The Investigator must certify that the data entered are complete and accurate.

After final database lock, the investigator will receive copies of the patient data for archiving at the investigational site.

11.2 Database management and quality control

Novartis personnel (or designated CRO) will review the data entered by investigational staff for completeness and accuracy. Electronic data queries stating the nature of the problem and requesting clarification will be created for discrepancies and missing values and sent to the investigational site via the EDC system. Designated investigator site staff are required to respond promptly to queries and to make any necessary changes to the data.

Concomitant treatments and prior medications entered into the database will be coded using the World Health Organization (WHO) Drug Reference List, which employs the Anatomical Therapeutic Chemical classification system. Medical history/current medical conditions and adverse events will be coded using the Medical Dictionary for Regulatory Activities (MedDRA) terminology.

Select laboratory samples will be processed centrally and the results will be sent electronically to Novartis (or a designated CRO).

For echocardiograms, a dedicated imaging CRO will collect all randomized patient echo data from sites and provide analysis by a central reader. The analysis results will be sent electronically to Novartis (or a designated CRO).

Randomization codes and data about all study treatment (s) dispensed to the patient and all dosage changes will be tracked using an Interactive Response Technology (IRT). The system will be supplied by a vendor, who will also manage the database. The data will be sent electronically to Novartis (or a designated CRO) at specific timelines.

Each occurrence of a code break via IRT will be reported to the clinical team and monitor. The code break functionality will remain available until study shut down or upon request of Novartis.

Once all the necessary actions have been completed and the database has been declared to be complete and accurate, it will be locked and the treatment codes will be unblinded and made available for data analysis to be accessed by independent programmer and statistician. Any changes to the database after that time can only be made after written agreement by Novartis development management.

11.3 Site monitoring

Before study initiation, at a site initiation visit or at an investigator's meeting, a Novartis representative or designated CRO will review the protocol and data capture requirements (i.e. eSource DDE or eCRFs) with the investigators and their staff. During the study, Novartis employs several methods of ensuring protocol and GCP compliance and the

quality/integrity of the sites' data. The field monitor will visit the site to check the completeness of patient records, the accuracy of data capture / data entry, the adherence to the protocol and to Good Clinical Practice, the progress of enrollment, and to ensure that study treatment is being stored, dispensed, and accounted for according to specifications. Key study personnel must be available to assist the field monitor during these visits. Continuous remote monitoring of each site's data may be performed by a centralized Novartis CRA or designated CRO staff. Additionally, a central analytics organization may analyze data & identify risks & trends for site operational parameters and provide reports to Novartis clinical teams to assist with trial oversight.

The investigator must maintain source documents for each patient in the study, consisting of case and visit notes (hospital or clinic medical records) containing demographic and medical information, laboratory data, electrocardiograms, and the results of any other tests or assessments. All information on CRFs must be traceable to these source documents in the patient's file. The investigator must also keep the original informed consent form signed by the patient (a signed copy is given to the patient).

The investigator must give the monitor access to all relevant source documents to confirm their consistency with the data capture and/or data entry. Novartis monitoring standards require full verification for the presence of informed consent, adherence to the inclusion/exclusion criteria, documentation of SAEs, and of data that will be used for all primary variables. Additional checks of the consistency of the source data with the CRFs are performed according to the study-specific monitoring plan. No information in source documents about the identity of the patients will be disclosed.

12 Data analysis and statistical methods

Any data analysis carried out independently by the investigator should be submitted to Novartis before publication or presentation.

12.1 Analysis sets

For all analysis sets, patients will be analyzed according to the study treatment(s) received. The safety analysis set will include all patients that received any study drug. The randomized analysis set (RAS) will consist of all randomized patients. The per-protocol set (PPS) will be a subset of the RAS that will consist of all randomized patients who have no major protocol deviations with relevant impact on PD/efficacy data and whom are at least 80% compliant with study drug administration. PD/efficacy variables will be analyzed based on the PPS.

12.2 Subject demographics and other baseline characteristics

Baseline will be defined as the last non-missing assessment prior to the first dose of study drug, unless specified otherwise.

Demographic and other baseline data including disease characteristics will be listed and summarized descriptively by treatment group for the RAS. Categorical data will be presented as frequencies and percentages. For continuous data, mean, standard deviation, median, minimum, and maximum will be presented. Relevant medical histories and current medical

conditions at baseline will be summarized by system organ class and preferred term, by treatment group.

12.3 Treatments

Concomitant medications and significant non-drug therapies prior to and after the start of the study treatment will be listed and summarized according to the Anatomical Therapeutic Chemical (ATC) classification system by treatment for the RAS.

12.4 Analysis of the primary endpoint(s)

12.4.1 Definition of primary endpoint(s)

The primary endpoint will be the change from baseline in peak VO₂ (ml/kg/min) at week 50, where baseline peak VO₂ will come from the screening/baseline CPET.

12.4.2 Statistical model, hypothesis, and method of analysis

The primary analysis will assess the effect of LCZ696 on the change from baseline in peak VO₂ at week 50 compared to placebo. A longitudinal mixed effects model for the change from baseline will be used. The model will include treatment, time (as a categorical variable), and the treatment-by-time interaction as fixed effects, patient as a random effect, and baseline peak VO₂ as a covariate. The least-squares (LS) mean and associated 90% confidence interval (CI) for the change from baseline in peak VO₂ for each treatment, and the estimated mean treatment difference, the p-value, and the corresponding 2-sided 80% CI will be extracted from the model at each time point.

12.4.3 Handling of missing values/censoring/discontinuations

There will be no imputation of missing data. The primary model implicitly imputes missing measurements under a missing at random assumption.

12.4.4 Sensitivity and Supportive analyses

Three supportive analyses will be performed to further assess the effect of LCZ696 on changes in peak VO₂:

- (1) An analysis of the change from baseline in % of predicted peak VO₂. The same model as described for the primary endpoint will be used.
- (2) An analysis of the ratio to baseline in peak VO₂. A similar model as described for the primary analysis will be used, but with ratio to baseline as the response, and all peak VO₂ measurements will be log transformed prior to analysis.
- (3) The primary analysis performed on the RAS.

12.5 Analysis of secondary endpoints

12.5.1 Safety endpoints

All safety analyses will be presented separately for the run-in period and the double-blind period using the safety set. All listings and tables will be presented by treatment.

Adverse events

All information obtained on AEs will be displayed by treatment and patient. The number (and percentage) of patients with treatment emergent AEs (events started after the first dose of study medication or events present prior to start of double-blind treatment but increased in severity based on preferred term) will be summarized in the following ways:

- by treatment, primary system organ class, and preferred term.
- by treatment, primary system organ class, preferred term, and maximum severity.
- by treatment, Standardized MedDRA Query (SMQ), and preferred term.

A patient with multiple adverse events within a primary system organ class is only counted once towards the total of the primary system organ class.

Vital signs

All vital signs data will be listed by treatment, patient, and visit/time and if ranges are available, abnormalities (and relevant orthostatic changes) will be flagged. Summary statistics will be provided by treatment and visit/time.

[figure not shown]
12-lead ECG

All ECG data will be listed by treatment, patient, and visit/time, and abnormalities will be flagged. Summary statistics will be provided by treatment and visit/time.

Clinical laboratory evaluations

All laboratory data will be listed by treatment, patient, and visit/time and if normal ranges are available abnormalities will be flagged. Summary statistics will be provided by treatment and visit/time. Shift tables using the low/normal/high classification will be used to compare baseline to the worst on-treatment value.

12.7 Interim analyses

An interim analysis for safety and efficacy will be performed when approximately 20 patients have completed the Week 26 CPET assessment. The same analysis described for the primary analysis will be performed using all the available CPET data at the time of the interim database freeze. Unblinded results will be reviewed by the clinical team. The clinical team may communicate the results (e.g., evaluation of PoC criteria or information needed for planning/modifying another study) to relevant Novartis teams for information, consulting, and/or decision purposes. Additional interim analyses may be conducted to support decision making concerning the current clinical study, the sponsor's clinical development projects in general, or in case of any safety concerns.

12.8 Sample size calculation

12.8.1 Primary endpoint(s)

Approximately forty-four (44) patients will be enrolled in the study with the anticipation that at least 40 patients complete the study. With 40 completers, there will be 80% power to achieve

an efficacy criteria of at least 50% confidence that LCZ696 increases peak VO₂ by at least 3 ml/kg/min over placebo, provided that the true effect of LCZ696 is at least a 4.15 ml/kg/min increase over placebo and the standard deviation of the change from baseline is 4.25 ml/kg/min (Olivotto et al 2018). If LCZ696 is not different from placebo, there will be a 1.5% chance of achieving the efficacy criteria (i.e., the false positive rate will be 1.5%). For the interim analysis, with week 26 data from at least 20 patients, there will be 70% power to meet the efficacy criteria under the same assumptions, and a 6% false positive rate if there is no increase over placebo.

13 Ethical considerations and administrative procedures

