Potassium	≤ 5.2 mmol/L (mEq/L)	≤ 5.4 mmol/L (mEq/L)
eGFR	≥ 30 mL/min/1.73m ²	≥ 25 mL/min/1.73m ²
Blood Pressure	SBP ≥ 100 mmHg	No symptomatic hypotension as determined by the investigator and SBP ≥ 100 mmHg
AEs / Med History	No conditions that preclude continuation according to the eligibility criteria	No AEs that preclude continuation according to the investigator's judgment

Note that for abnormalities in potassium and eGFR, laboratory values should be repeated to confirm abnormality as outlined in protocol Section 16.3 and Section 16.4. For out-of-range blood pressure readings, measurement may be repeated up to two times as detailed in the Site Operations Manual and protocol Section 16.5.

Patients will receive study treatment for ~50 weeks, which includes the 4-week treatment run-in period, with dose tolerability being assessed at each visit as well as at unscheduled visits (as necessary) and through feedback that patients may provide between visits. Safety and tolerability assessments will include physical examinations, ECGs, vital signs, standard clinical laboratory evaluations (hematology and blood chemistry), AE and SAE monitoring. At week 26 and week 50, patients will have follow-up CPET [REDACTED]. No further treatment will be provided after the week 50 visit, and patients will return to the study center ~30 days later for final safety and EOS evaluations.

Figure 1-1 Study design

2 First interpretable results (FIR)

First interpretable results (FIR) will be provided for this trial at the IA and at the end of study (CSR).

The study FIR template (mock slides) can be found in SubWay in the study Statistics folder.

The template shows the analysis / results to be presented in the FIR. Study outputs required to be created at the time of the FIR will be highlighted in TFL shells document and marked as “Key” in the Programming Deliverables Tracker (PDT) output list.

3 Interim analyses

An interim analysis for safety and efficacy was performed when approximately 20 patients had completed the Week 26 [REDACTED]. [REDACTED]
[REDACTED]
[REDACTED]

[REDACTED] Unblinded results were reviewed by the clinical team. The clinical team may communicate the results (e.g., evaluation of PoC criteria or information needed for

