planning/modifying another study) to relevant Novartis teams for information, consulting, and/or decision purposes. If early efficacy is demonstrated, enrollment of the study may be stopped. No other changes to the design of the study are anticipated as a result of the analysis.

Additional interim analyses may be conducted to support decision making concerning the current clinical study, the sponsor's clinical development projects in general, or in case of any safety concerns.

4 Statistical methods: Analysis sets

For all analysis sets, patients will be analyzed according to the study treatment(s) received.

Throughout this document, 'treatment' refers to one of the two randomized treatment arms assigned to each patient at the Day 29/Week 4 visit, i.e., LCZ696 or Placebo. For the safety analyses that will be presented separately for the treatment run-in period, 'treatment' refers to the corresponding treatments given during the treatment run-in period, i.e. placebo b.i.d. for 2 weeks followed by 50 mg p.o. b.i.d. of active LCZ696 for 2 weeks.

Unless specified otherwise, baseline will be defined as the last non-missing assessment prior to the first dose of study drug administered at the Day 1 visit.

The **safety analysis set** will include all patients that received any study drug.

The **randomized analysis set (RAS)** will consist of all randomized patients.

The **per-protocol analysis set (PPS)** will be a subset of the RAS that will consist of all randomized patients who have no major protocol deviations with relevant impact on PD/efficacy data and who are at least 80% compliant with the overall study drug administration.

The definition for the overall compliance to the study drug administration is provided in [Section 7.2](#).

The analysis sets and protocol deviation codes are related as follows:

Table 4-1 Protocol deviation codes and analysis sets

Category Deviation code	Text description of deviation	Data exclusion
	Patients are excluded from safety analysis in case of these PDs:	Exclude patient from safety analysis set
	Patients are excluded from RAS analysis in case of these PDs:	Exclude patient from randomized analysis set
	Patients are excluded from PD/efficacy analysis in case of these PDs:	Exclude patient from per-protocol analysis set

Category Deviation code	Text description of deviation	Data exclusion

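### Is the 1.5% false-positive rate misleading, given that the same criterion is also applied at an interim that may stop enrolment?

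*Protocol*

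**What the plan says.** Protocol 12.8.1 defines success as at least 50% confidence that the drug raises peak VO₂ by 3 ml/kg/min or more over placebo. The calculation opens with "With 40 completers, there will be 80% power to achieve" that criterion, for a true effect of 4.15 and a standard deviation of 4.25. The next sentence, on the case of no effect, ends with "the false positive rate will be 1.5" per cent. A separate sentence covers the interim with Week 26 data from at least 20 patients: 70% power and "a 6% false positive rate if there is no increase over placebo".

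Protocol 12.4.1 fixes the time point: "The primary endpoint will be the change from baseline in peak" VO₂ at Week 50. SAP 6.1.1 and 6.1.4 agree.

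Protocol 12.7 says the interim repeats the primary analysis. Its results may go to the sponsor's teams, for example as "evaluation of PoC criteria or information needed for planning/modifying another study". It adds: "Additional interim analyses may be conducted to support decision making concerning the current clinical study". Protocol 6.4 describes the sharing of unblinded interim information as being for internal decisions.

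SAP Section 3 reports that the interim has taken place ("An interim analysis for safety and efficacy was performed when approximately 20 patients had completed the Week 26" assessment) and states: "If early efficacy is demonstrated, enrollment of the study may be stopped". Parts of the interim text in Protocol 4.6 and SAP Section 3 are blacked out.

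**The concern.** One criterion is applied twice, and the first application can shrink the sample for the second. A stop after a favourable interim leaves fewer than 40 completers at Week 50. The early patients whose Week 26 results triggered the stop then weigh more in the Week 50 estimate. Both effects raise the chance that a null drug passes.

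The readable text does not say whether an interim pass counts as meeting the criterion. It gives no Week 50 error rate or power after a stop, and it allows further interims without fixing their number. A reader could therefore hold the final result against 1.5% and 80% when neither applied. If an interim pass were presented as proof of concept, the relevant error would be 6% or more, about four times 1.5%.

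**Working it through.** **Inputs.** From Protocol 12.8.1: threshold 3, true effect 4.15, SD 4.25, 40 completers at the final look, 20 patients at the interim. Allocation is 1:1 (Protocol Section 3). Fifty per cent confidence of an effect of at least 3 means that the point estimate must be at least 3. Not given, and therefore assumed: the within-patient correlation ρ of the Week 26 and Week 50 changes, the number of completers after a stop, and that the stop uses the same threshold of 3.

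**1. The plan's own figures.** SE = 4.25 × √(2/n per arm).
- Final, 20 per arm: SE = 4.25 × √0.1 = 1.344. Power = Φ((4.15 − 3)/1.344) = 80.4%. False-positive rate = P(Z > 3/1.344) = 1.28%, or 1.58% from a t distribution with 38 df. The printed 80% and 1.5% agree with this.
- Interim, 10 per arm: SE = 4.25 × √0.2 = 1.901. False-positive rate = P(Z > 3/1.901) = 5.7%, or 6.6% from t with 18 df; printed 6%. Power = Φ(1.15/1.901) = 72.7%; printed 70%, so slightly cautious.

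Each printed rate is therefore a single-look figure for the sample size named with it.

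**2. A pass at either look counts.** The two estimates have correlation ρ√(20/40). Under no effect, the chance that at least one reaches 3 is 6.93% at ρ = 0 (check: 1 − 0.9428 × 0.9872 = 6.93%), 6.70% at ρ = 0.5, 6.32% at ρ = 0.9 and 6.20% at ρ = 1. The printed rates alone bound it between 6.0% (the larger) and 7.5% (the sum).

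**3. Only Week 50 counts, and every interim pass stops enrolment.** The no-stop rate of 1.28% rises by 5.72% (a false interim pass) times the increase in the chance that Week 50 also passes. After a false interim pass, that chance with 40 completers is 5.4% at ρ = 0.5 and 11.9% at ρ = 0.9.

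| Completers after a stop | Week 50 pass after a false interim pass (ρ = 0.5 / 0.9) | Overall Week 50 false-positive rate | Overall power |
|---|---|---|---|
| 40 (no reduction) | 5.4% / 11.9% | 1.28% | 80.4% |
| 36 | 7.2% / 16.2% | 1.39% / 1.53% | 79.8% / 80.2% |
| 30 | 11.4% / 26.2% | 1.63% / 2.10% | 78.9% / 80.2% |
| 26 | 15.7% / 36.8% | 1.87% / 2.71% | 78.3% / 80.4% |
| 20 | 25.8% / 64.7% | 2.45% / 4.30% | 77.5% / 81.6% |

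Example, 30 completers at ρ = 0.9: 1.28 + 5.72 × (0.262 − 0.119) = 1.28 + 0.82 = 2.10%. Simulations of 1,000,000 trials per setting gave the same false-positive rates within 0.1 percentage points.

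**4. Which rows are plausible.** Randomisation is at Week 4, so a patient needs 22 more weeks to reach Week 26. The bottom row requires that nobody beyond the first 20 contributes a Week 50 result, although recruitment could continue throughout that wait. The documents give no accrual rate, so the other rows cannot be ranked precisely.

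**The case for a change.** The strongest case for a change is that two separate rates do not tell a reader which one governs a success claim. Protocol 12.7 mentions proof-of-concept criteria at the interim, so the reading in which either look counts is not expressly excluded. Even on the Week 50 reading, the rate with 30 completers is up to 2.10/1.28 = 1.6 times the no-stop value. After a false interim pass, Week 50 also passes in 11–26% of trials with 30 completers, against 5–12% with 40. A sentence would settle the matter at almost no cost.

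Part of this stands. The readable text does not say that Week 50 alone decides, nor what the Week 50 error is after a stop.

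The rest is weaker. The 1.5% follows directly from a sentence that begins with the 40 completers, and the interim has its own sentence with its own sample size, power and error. Anyone who treats an interim pass as proof of concept already has the applicable 6%; adding the final look takes the computed 5.7% to 6.2–6.9%. Protocol 6.4 and 12.7 direct interim results to internal use, and SAP Section 3 permits a stop of enrolment, not a declaration of success. No success claim is attached to the further interims. The Week 50 figures also take every interim pass to stop enrolment, where the SAP says only that it may. A stricter bar, which the blacked-out lines could contain, would lower them.

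**Conclusion.** The concern identifies an unstated policy, not an error in the rates. The printed 1.5% and 6% are right for their own looks, and neither is presented as a combined rate. With the primary endpoint at Week 50, an analyst would judge success there. On that reading an early stop moves the false-positive rate from 1.28% to 1.4–1.5% with 36 completers and to 1.6–2.1% with 30, with overall power between 78.9% and 80.2%. The larger values, 2.4–4.3%, need a sample frozen at 20.

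That size of movement is tolerable in a Phase II study that reports 80% intervals for the treatment difference and judges success on a 50% confidence criterion. The Week 50 standard error and interval will reflect the completers actually obtained, although they do not correct for selection at the interim. Whether enrolment stopped, and with how many completers, is a matter for the study report.

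An added label would alter no analysis, threshold or result, and the interim has already been performed, so no change to the plan follows. The conclusion rests on the assumed correlation of 0.5 to 0.9, the assumed completer numbers, a stopping threshold equal to the success threshold, and the readable part of the interim text.
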